### **9.3.3 Removal of Subjects from Treatment or Assessment**

Subjects may withdraw their consent to participate in the study at any time without prejudice. The Investigator must withdraw from the study any subject who requests to be withdrawn. Such subjects will always be asked about the reason(s) for withdrawal. The Investigator will discuss with the subject appropriate procedures for withdrawal from the study. The Investigator should ask the subject's consent to perform the procedures listed under the early termination visit. Should a subject withdraw from the study, all efforts will be made to complete and report the observations as thoroughly as possible up to the date of the withdrawal.

A subject's participation in the study may be discontinued at any time at the discretion of BioMarin or of the Investigator and in accordance with his/her clinical judgment. When possible, the tests and evaluations listed for the termination visit should be carried out and every effort will be made to gather follow-up safety data if possible.

BioMarin must be notified of all subject withdrawals as soon as possible. BioMarin also reserves the right to discontinue the study at any time for either clinical or administrative reasons and to discontinue participation by an individual Investigator or site for poor enrollment or noncompliance.

Reasons for which the Investigator or BioMarin may withdraw a subject from the study include, but are not limited to, the following:

- Subject requires medication or medical procedure prohibited by the protocol
- Subject does not adhere to study requirements specified in the protocol
- Subject was erroneously enrolled into the study or does not meet entry criteria and not yet been dosed with BMN 270; subjects who do not meet entry criteria but who erroneously receive BMN 270 should remain in the study for safety monitoring
- Subject is lost to follow-up

If a subject fails to return for scheduled visits, a documented effort must be made to determine the reason. If the subject cannot be reached by telephone, a certified letter should be sent to the subject requesting contact with the Investigator. This information should be recorded in the study records.

The Investigator or designee must explain to each subject, before enrollment into the study, that for evaluation of study results, the subject's protected health information obtained during the study may be shared with the study Sponsor, regulatory agencies, and IRB/IEC/REB. It is the Investigator's (or designee's) responsibility to obtain written permission to use protected

health information per country-specific regulations, such as the Health Insurance Portability and Accountability Act (HIPAA) in the US, from each subject. If permission to use protected health information is withdrawn, it is the Investigator's responsibility to obtain a written request, to ensure that no further data will be collected from the subject and the subject will be removed from the study.

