
Subjects who do not respond to BMN 270 treatment (ie, treatment failure, manifesting as either failure to achieve FVIII activity <math>\geq</math> 5 IU/dL by Week 52 or inability to maintain independence from prophylactic FVIII replacement therapy due to joint bleeding episodes, in the judgment of the Investigator) may, at the Investigator's discretion and after discussion with the Medical Monitor or Sponsor-designated Data Monitor, follow an abbreviated visit schedule after Week 52 of the study by attending only the Q12W and End of Year visits during Years 2-5.
 
There will be an ongoing review of individual subject safety by the Medical Monitor, and both safety and efficacy data by the DMC. Therapeutic oral corticosteroids may be initiated when a subject's ALT values are elevated, and subsequent dosage adjustments made, after consultation between the Investigator and the Medical Monitor.
 
Any safety signal may trigger a review of the data and possible additional immunogenicity studies or other diagnostics deemed necessary that include an assessment of cellular immune responses using collected peripheral blood mononuclear cells (PBMCs).
		

NUMBER OF SUBJECTS PLANNED: Approximately 40 subjects may enroll into the study.
		

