### **9.3.4 Subject Identification and Replacement of Subjects**

Each subject will be assigned a unique subject identifier. This unique identifier will be on all eCRF pages. In legal jurisdictions where use of initials is not permitted, a substitute identifier will be used.

Subjects who withdraw from the study after receiving BMN 270 will not be replaced.

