#### **9.4.8 Prior and Concomitant Medications**

All prescription and over-the-counter medications (including dietary and herbal supplements) taken by a subject for 30 days before Screening will be recorded on the designated eCRF.

The Investigator may prescribe additional medications, deemed necessary to provide adequate prophylactic or supportive care, during the study, as long as the prescribed medication is not prohibited by the protocol. In the event of an emergency, any needed medications may be prescribed without prior approval, but the Medical Monitor must be notified of the use of any contraindicated medications immediately thereafter. Any concomitant medications added or discontinued during the study should be recorded on the eCRF. Medications should, whenever possible, not be recorded in the electronic database with a frequency of PRN.

The following medications are prohibited starting 30 days before Screening and through the end of the study, and the Sponsor must be notified if a subject receives any of these during the study:

- Any investigational therapy
- Systemic immunosuppressive agents, except for corticosteroids
- Emicizumab
- Fitusiran
- Concizumab
- Efavirenz
- Lamivudine

The following medications should be avoided, starting 30 days prior to and for at least 52 weeks after BMN 270 infusion and minimized throughout the remaining duration of the study.

- Alcohol
- Herbal and natural remedies and dietary supplements
- Medications which may be hepatotoxic

Vaccines should also be avoided during this period, but in particular during the first 26 weeks unless clinically indicated.

The following medications should be avoided during oral corticosteroid therapy:

- Vaccines
- NSAIDs

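### Section 9.3.3 permits withdrawing already-dosed subjects for a prohibited medication or non-adherence, which after a single infusion can only end their follow-up

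*Protocol*

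**What the plan says.** Protocol Section 9.3.3 introduces an open-ended, permissive list: "Reasons for which the Investigator or BioMarin may withdraw a subject from the study include, but are not limited to, the following". The first two entries are "Subject requires medication or medical procedure prohibited by the protocol" and "Subject does not adhere to study requirements specified in the protocol". Neither separates subjects before infusion from subjects after it. The third entry, on erroneous enrollment, does: undosed subjects may be withdrawn, but "subjects who do not meet entry criteria but who erroneously receive BMN 270 should remain in the study for safety monitoring". A separate clause in the same section lets the sponsor or the investigator discontinue a subject at any time at their discretion. When that happens, termination-visit tests are done when possible and "every effort will be made to gather follow-up safety data if possible".

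Section 9.4.8 sets the scope of the first reason: "The following medications are prohibited starting 30 days before Screening and through the end of the study". The list covers investigational therapy, systemic immunosuppressants other than corticosteroids, emicizumab, fitusiran, concizumab, efavirenz and lamivudine. The only consequence stated there is that the sponsor must be told.

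Under Section 9.3.4, "Subjects who withdraw from the study after receiving BMN 270 will not be replaced". Under the Synopsis, subjects who meet the treatment-failure definition may "follow an abbreviated visit schedule after Week 52 of the study by attending only the Q12W and End of Year visits" during Years 2-5, so they stay under observation.

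**The concern.** In most trials these two reasons protect a subject from further dosing or protect the integrity of a continuing regimen. Here there is nothing left to stop after Day 1. The vector has been given, and the protocol describes expression as potentially life-long. Taking a dosed subject off study removes only the scheduled liver, inhibitor, shedding and FVIII activity tests and the diary record of bleeds and FVIII use.

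Long-term safety is a stated objective (Section 8). Some agents on the prohibited list are alternative hemophilia treatments or immunosuppressants, so a subject with a poor response or an immune complication could be among those to whom the first reason applies. If so, missingness in the Week 5-52 endpoints and in the five-year safety record would be related to outcome. Withdrawn subjects are not replaced, and Section 14.7 states no dropout allowance.

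**Working it through.** 1. Effect of withdrawal after dosing. The Synopsis gives treatment duration as a single infusion. After Day 1, withdrawal from treatment has no meaning; only withdrawal from observation remains.

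2. The rules side by side.
- Section 9.3.3, first two reasons: a dosed subject may be taken off study.
- Section 9.3.3, third reason: a dosed subject who should never have been enrolled stays, for safety. That rationale applies equally to an eligible dosed subject.
- Section 9.4.8: prohibited use leads to notification, which is compatible with continued participation.
- Synopsis, Table 9.1.5 (footnote on treatment failure) and Section 12.7: failures remain on reduced visits through Year 5, and those still shedding vector keep giving samples.
- Section 10.3.1: AE reporting runs about 5 years or to discontinuation, whichever is longer. Read literally, it would not stop at withdrawal.

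 These rules are not in strict contradiction, because the first is a discretion. They do point in different directions for the same subject.

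3. What survives withdrawal. Data to that date are kept. A termination visit is requested (Section 12.8), existing AEs are followed (Section 10.6), and later deaths or SAEs thought related, cancers and congenital anomalies are to be notified (Section 10.7). Scheduled testing stops. For analysis, every dosed subject is in ITT, and every HIV-negative one in mITT (Section 14.8). A missing primary value takes the median of the last 4-week window with valid data (Section 14.2). For FVIII use and ABR, Section 14.3 offers observed-case sensitivity analyses and possible multiple imputation, but no main-analysis rule for a subject who leaves before Week 52. The supplied SAP is for a one-subject interim analysis by listings and its efficacy text is not visible, so I infer nothing from it.

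4. The plan's own figure. First secondary endpoint, Synopsis: n = 35, effect size 0.6, one-sample t-test, two-sided 0.05. The noncentrality is 0.6 × √35 = 3.55 on 34 df, giving power of 93.2%, so the stated minimum of 90% is reproduced. (Section 14.7 gives the level as 0.025, where power is 88.0%. That discrepancy is separate from this point.)

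5. Power if withdrawn subjects contributed nothing, an extreme that the plan does not state, with the effect size unchanged: n = 32 gives 90.8%, n = 31 gives 89.8%, n = 28 gives 86.4%. Four of 35 subjects (11.4%) would have to vanish before power fell below 90%.

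6. Observation lost by one subject who leaves at Week 20 (an assumed time). Weeks 5-52 are 48 weeks: (52 − 20)/48 = 32/48 = 67%. Follow-up to Week 260: (260 − 20)/260 = 240/260 = 92%.

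7. ABR bias under assumed inputs: 35 subjects, baseline ABR 3.5, non-failures at 1 after infusion.
- Two failures at ABR 10 contribute no data. The full mean is (33 × 1 + 2 × 10)/35 = 1.51, a change of −1.99. Without them the change is 1 − 3.5 = −2.50, a shift of 0.51 bleeds/year in favor of BMN 270. For 1 to 5 failures with ABR 4 to 20, the shift is 0.09 to 2.71.
- The same two failures instead contribute annualized data to Week 20 (16 weeks at rate 10) and would have run at rate 1 on another agent for the remaining 32. The full-window rate is (10 × 16 + 1 × 32)/48 = 4.0; the truncated rate is 10. The shift is 2 × (10 − 4)/35 = 0.34 against BMN 270.

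The sign therefore depends on a rule that Section 14.3 does not give.

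**The case against.** A reader might infer that Section 9.3.3 removes treatment failures from the data. The documents do not support that. Withdrawal is optional, treatment failure is not a listed reason, and no section requires withdrawal after a prohibited medication. For recurrent bleeding, the protocol's own route is a discussion of resuming FVIII prophylaxis (Section 9.7.3.1), and FVIII is not on the prohibited list. Efavirenz and lamivudine have no evident link to failure. That failures are likely to need a listed agent is plausible, but it is an assumption.

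It can also be said that a discretion covering all subjects and a retention rule for wrongly dosed ones are asymmetric rather than contradictory; that the abbreviated schedule begins only after Week 52 and so does not bear on an exit at Week 20; and that best-effort safety collection continues after withdrawal. With one subject enrolled and only listings planned, the 35-subject argument affects no analysis now.

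All of this stands, and it limits the point. It does not explain why two reasons that stop no treatment should be available after infusion, and it does not supply the missing Week 5-52 rule.

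**Conclusion.** The point holds in a limited form. Section 9.3.3 permits, without requiring, the early end of scheduled follow-up for dosed subjects who need a prohibited medication or procedure or who do not adhere. This may include failures who move to a listed agent. Safety data would then be collected only on a best-effort basis, and the handling of Week 5-52 FVIII use and ABR is unstated. The wording sits inconsistently beside the retention of wrongly dosed subjects, the notify-only rule in Section 9.4.8 and the retention of failures in Years 2-5.

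The observation lost could be large for an individual: 67% of endpoint weeks and 92% of follow-up weeks, if he left at the assumed Week 20. Neither the size nor the direction of an efficacy bias is established; the shifts above rest on assumed failure counts and bleeding rates. At present the effect is confined to the long-term follow-up of the one enrolled subject, whose record is all of this study's post-dose data.

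**What to change.** In Section 9.3.3, apply the dosed/undosed distinction already used for erroneous enrollment to the prohibited-medication-or-procedure and non-adherence reasons, so that after infusion neither is by itself a reason to end study follow-up. Record the medication with dates, notify the sponsor as Section 9.4.8 already requires, and continue scheduled visits with the subject's consent. Qualify the general discretion clause and the open-ended lead-in in the same way.

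Keep the exits the protocol already provides: withdrawal of consent, withdrawn permission to use health data, loss to follow-up, transfer to another BMN 270 study, and site or study closure. Reconcile Section 9.3.3 with Section 9.4.8, Section 10.3.1 and the treatment-failure footnote to Table 9.1.5. State how FVIII use and ABR are derived when observation ends before Week 52, and flag data collected after a prohibited medication. No change to permitted medications or treatment rules is proposed.

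The cost is amendment wording and its ethics review. Visits are already scheduled to Week 260. The small downside is that data gathered while a subject is on another agent reflect that agent too and must be flagged in analyses or listings.

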### **9.3.3.1 Study Safety Evaluation Criteria**

If any of the following events occur in a subject in the study who has received BMN 270 infusion, an urgent evaluation by the DMC will be required and further enrollment into the trial will be temporarily put on hold if recommended by the DMC per Section 9.1.

1. Liver dysfunction (criteria do not apply to ALT elevations with an extra-hepatic etiology):
  - o ALT > 5x ULN, for more than 2 weeks
  - o ALT > 3x ULN **and** (total bilirubin >2x ULN **or** INR >1.5)
  - o ALT > 3x ULN with signs and symptoms of liver dysfunction
2. The occurrence of Grade 4 or Grade 5 adverse events assessed as related to study drug (events of liver dysfunction are defined above).
3. The occurrence of an AE of hepatic failure.
4. The detection of high-titer neutralizing antibodies (>5 BU) to hFVIII following BMN 270 infusion in two subjects.
5. The occurrence of any cancer (except non-melanoma skin cancer) at any point after BMN 270 infusion.
6. The occurrence of a thromboembolic event with FVIII activity > 150 IU/dL in one subject.

If any of the following events occurs in a subject in the study who has received BMN 270 infusion, an urgent evaluation by the DMC will be required. Further enrollment into the trial will continue while DMC evaluation is ongoing, unless deemed otherwise by the DMC:

1. The detection of high-titer neutralizing antibodies (>5 BU) to hFVIII following BMN 270 infusion in one subject.
2. Occurrence of a thromboembolic event in one subject.

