## **10.2 Serious Adverse Events**

A serious adverse event (SAE) is any untoward medical occurrence that, at any dose:

- Results in death
- Is life-threatening
- *Note: Life-threatening refers to an event in which the subject was at risk of death at the time of the event. It does not refer to an event, which hypothetically might have caused death, if it were more severe.*
- Requires inpatient hospitalization or prolongation of existing hospitalization

Note: In general, hospitalization signifies that the subject has been detained (usually involving at least an overnight stay) at the hospital or emergency ward for observation and/or treatment that would not have been appropriate in the physician's office or outpatient setting. If the investigational product preparation, infusion, and post-infusion observation period require transfer to an inpatient setting for completion, in the absence of an AE, this will not be considered an SAE (refer to Section 10.4.1.7).

Complications that occur during hospitalization are AEs. If a complication prolongs hospitalization, the event is serious.

Hospitalization for elective treatment of a pre-existing condition that did not worsen from baseline is not considered an AE.

- Results in persistent or significant disability or incapacity
- Is a congenital anomaly or birth defect in the child or fetus of a subject exposed to IP prior to conception or during pregnancy

- Is an important medical event or reaction – that, based on medical judgment, may jeopardize the subject or require medical/surgical intervention to prevent one of the other outcomes listed above (eg, anaphylaxis)

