14.1.5 Events of Special Interest (EOSIs)

The following events of special interest, which include EOSI defined in the protocol, will be provided in a data listing for each type of EOSI.

- Transaminitis
 - ALT elevations (AE Preferred term: “Alanine aminotransferase increased”).
 - AEs of liver dysfunction, defined using the MedDRA search strategy high level term (HLT = “Liver function analyses”).
 - Potential Hy’s law cases
 - ALT or AST \geq 3x ULN and serum TBL > 2x ULN
 - Assessments of ALT/AST and TBL must be on the same day

A listing will be provided.

- Infusion related reaction, Hypersensitivity, Anaphylactic or Anaphylactoid reactions
 - Infusion related reactions, defined as AEs occurring during BMN 270 infusion or up to 48 hours post-infusion^a, will be summarized as follows:

- Subjects who receive infusion with initial rate of approximately 4 mL/min
- The rest of the subjects, i.e. subjects who receive infusion with initial rate of 1 mL/min
- All treated subjects
- Systemic hypersensitivity (Hypersensitivity [SMQ] - narrow scope), occurring during BMN 270 infusion or up to 48 hours post-infusion^a.
- Anaphylactic, or anaphylactoid reactions (Anaphylactic reaction [SMQ] – algorithmic), occurring during BMN 270 infusion or up to 48 hours post-infusion^a – listing only.
- Thromboembolic events:
 - Embolic and thrombotic events (SMQ).
 - AEs suggestive of thromboembolic events: for subjects who have FVIII elevation > 150% any time during study, a listing of clinical terms suggestive of thromboembolic events observed from the time point prior to when FVIII was elevated until FVIII falls below 150%. (The AE preferred terms are listed in Appendix 19.2.)
- Development of anti-FVIII neutralizing antibodies as measured by the Nijmegen modified Bethesda assay (Preferred term: "Anti factor VIII antibody positive", reported as EOSI)

^a If the number of hours post-infusion cannot be determined, AEs that start two days after the infusion day are excluded.

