14.2 Clinical Laboratory Tests

Clinical laboratory tests include blood chemistry, hematology, urine tests, and coagulation. A supportive listing of abnormal test values with CTCAE v4.03 grade 3 or greater will be produced.

Liver tests by central labs will be assessed on a regular basis, as detailed in the protocol. Summaries of ALT elevations including baseline ALT, time from infusion to ALT > ULN, ALT ≥ 3x ULN, ALT ≥ 5x ULN, ALT ≥ 1.5x ULN or (> ULN & > 2x baseline value), peak ALT level, duration of ALT elevation, corticosteroid treatments for ALT elevations including type, dose, time to initiation of treatment, and duration of treatment will be

provided. Correlation of ALT elevation to FVIII levels, as well correlation of steroid treatment to ALT elevation and FVIII levels will be presented in a listing. Local ALT assessments will be analyzed similarly as the central ALT assessments, if needed. Similar analyses will be applied to other liver tests including aspartate transaminase (AST), gamma-glutamyl transferase (GGT), lactate dehydrogenase (LDH), bilirubin, alkaline phosphatase (ALP), if needed.

In addition, incidences of potential drug-induced liver injury (DILI) that include an elevated ALT or AST in combination with either an elevated bilirubin or clinical jaundice, as defined by Hy's law, will be provided in a data listing.

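### The urgent-DMC liver criterion names ALT only, so an AST-led potential Hy's law case meets none of its laboratory limbs; within an ALT episode, PT/INR has no set repeat interval

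*Protocol*

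**What the plan says.** Protocol 9.3.3.1 gives three liver limbs that require urgent DMC evaluation:

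- ALT above 5x ULN for more than 2 weeks.
- The combined limb, "ALT > 3x ULN and (total bilirubin >2x ULN or INR >1.5".
- The symptom limb, "ALT > 3x ULN with signs and symptoms of liver dysfunction".

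The exemption is also worded for ALT: "criteria do not apply to ALT elevations with an extra-hepatic etiology". Criterion 2 is "The occurrence of Grade 4 or Grade 5 adverse events assessed as related to study drug (events of liver dysfunction are defined above", and criterion 3 is "The occurrence of an AE of hepatic failure".

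SAP 14.1.5 defines a potential Hy's law case as "ALT or AST \geq 3x ULN and serum TBL > 2x ULN", with both values on the same day. SAP 14.2 repeats the idea for drug-induced liver injury as "an elevated ALT or AST in combination with either an elevated bilirubin or clinical jaundice".

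AST is in every liver panel (Protocol Table 9.7.8.3.1); INR is not. PT/INR belongs to the coagulation screen (Table 9.7.8.2.1), whose timing is set in 12.5.5, 12.6.4 and 12.7.3. In the row of Table 9.7.8.3.2 for ALT at or above 3x ULN, liver tests continue at least twice weekly while ALT stays at that level. PT/INR is among the extra tests to obtain in that row, with no interval given.

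**The concern.** Section 9.3.3.1 is the protocol's rule for when liver injury must go to the DMC urgently. Each of its laboratory limbs starts from ALT. An injury in which AST leads and bilirubin is raised is one that the SAP itself singles out for listing, yet it meets no limb. Elsewhere the protocol does not set AST aside: exclusion criterion 3 uses the same 1.25x ULN limit for ALT and AST in defining significant liver dysfunction.

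The second matter is the INR arm of the combined limb. It works only if INR is measured while ALT is raised. If INR is normal at the work-up and rises later, without bilirubin above 2x ULN or symptoms, nothing in the work-up sets a time for the next measurement.

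At stake is how promptly the DMC reviews a treated subject. No endpoint or efficacy analysis is affected.

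**Working it through.** There is no stated figure to reproduce. The check compares the two rules on test cases and then sets out the test schedules.

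**1. The two rules on example cases.** The values are assumed; enzymes and bilirubin are multiples of ULN. No case has ALT above 5x, so the first limb never applies.

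| Case | ALT | AST | Bilirubin | INR | Symptoms | Limbs met in 9.3.3.1 | SAP 14.1.5 |
|---|---|---|---|---|---|---|---|
| A | 2.5 | 4 | 2.5 | 1.0 | no | 0 of 3 | yes |
| B | 2.5 | 4 | 2.5 | 1.8 | yes | 0 of 3 | yes |
| C | 3.0 | 3.0 | 2.5 | 1.0 | no | 0 of 3 | yes |
| D | 3.1 | 4 | 2.5 | 1.0 | no | 1 of 3 (combined) | yes |

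Cases A and B show the AST gap, and B shows that a raised INR and symptoms do not close it. Case D shows its limit: once ALT also passes 3x ULN, the combined limb fires. Case C shows the boundary difference. The trigger uses strictly above 3x ULN, while SAP 14.1.5, Table 9.7.8.3.2 and the steroid rule in 9.4.8.2 use at or above. That matters only at exactly 3.0x.

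With the combined limb rewritten as in the fix, all four cases trigger, and B also meets the rewritten symptom limb.

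**2. Other routes for case A.**

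- Criterion 3 applies if a hepatic-failure event is recorded, which is a later stage.
- Criterion 2 has two readings. If its parenthetical is a carve-out, liver events go back to the ALT limbs. If it is only a cross-reference, a related Grade 4 or 5 liver event triggers whatever the ALT. The laboratory values alone do not establish such an event.
- Section 15 gives the DMC ongoing review of individual data, but sets no urgent timing for this case.
- The sponsor would hear within 24 hours. ALT of 2.5x ULN is an event of special interest (10.2.1). The case might also be a serious event if, "based on medical judgment, may jeopardize the subject or require medical/surgical intervention" (10.2). Nothing in 10.5.1 passes either report to the DMC.
- Table 9.7.8.3.2 requires consultation with the Medical Monitor at ALT of 1.5x to below 3x ULN.

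**3. Scheduled PT/INR.**

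- Weeks 4, 10, 16, 22, 26, 32, 36, 44, 52: gaps 6, 6, 6, 4, 6, 4, 8, 8. Sum 48, mean 48/8 = 6.0 weeks. There is also a test at Week 2.
- Weeks 52, 76, 104, 128, 156, 180, 208, 232, 260: gaps alternate 24 and 28. Sum 208, mean 208/8 = 26.0 weeks.
- Year 2 routine liver panels between coagulation tests: 5 (Weeks 56, 60, 64, 68, 72), then 6 (Weeks 80, 84, 88, 92, 96, 100).

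**4. How often an episode contains a scheduled PT/INR.** Episode length is not in the documents, so take 2, 4 and 6 weeks. Assume visits on their nominal weeks and start times spread evenly. An episode of length L misses a scheduled test for (gap − L) weeks of start times in each gap longer than L.

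| L (weeks) | Liver panels required (2 per week) | No scheduled PT/INR, Weeks 4-52 | No scheduled PT/INR, Years 2-5 |
|---|---|---|---|
| 2 | 4 | (4+4+4+2+4+2+6+6)/48 = 32/48 = 67% | (22+26)/52 = 92% |
| 4 | 8 | (2+2+2+0+2+0+4+4)/48 = 16/48 = 33% | (20+24)/52 = 85% |
| 6 | 12 | (2+2)/48 = 8% | (18+22)/52 = 77% |

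These shares describe coverage by routine tests. They are not probabilities of a missed trigger: PT/INR is also obtained at the work-up, and INR need not rise. The INR gap is further confined to ALT above 3x and up to 5x ULN, or above 5x for up to 2 weeks, because a longer elevation above 5x triggers on ALT alone.

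**The case against.** The strongest reply is that ALT was chosen consistently. The steroid rule, the work-up, the event of special interest and the urgent trigger all run on ALT, and AST also rises from muscle. The Medical Monitor and the DMC review subjects on an ongoing basis, and under 9.1 any safety signal may prompt a data review. Investigators may order extra tests and repeat abnormal ones. The DMC Charter, which is not available here, may add duties. All of this stands and limits the consequence. It does not put AST into the rule that makes evaluation urgent.

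A reader might infer more than the documents support:

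- *That protocol and SAP conflict.* They do not. One is a trigger for action and the other a listing rule.
- *That an AST-led case cannot reach the DMC urgently.* It can as hepatic failure, and perhaps under criterion 2.
- *That INR is not rechecked, or that an episode requires no further INR.* PT/INR has an explicit schedule. From Week 2 to Week 36 no gap exceeds 6 weeks, so a 6-week episode starting before Week 36 reaches a scheduled test.
- *That the Years 2-5 spacing is the one that matters for the enrolled subject.* The SAP 19.1 windows run to Week 104, but a window table does not show his status. SAP 7 still plans to list whether he completed Weeks 26 and 52 or discontinued.

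**Conclusion.** The main point holds. A case with AST at or above 3x ULN, ALT at or below 3x ULN and bilirubin above 2x ULN is a potential Hy's law case in SAP 14.1.5 and meets 0 of the 3 liver limbs in 9.3.3.1. The secondary point holds in a narrow form. PT/INR is scheduled, but it has no repeat interval within an episode of ALT at or above 3x ULN, so a late rise may be seen late, mainly in short episodes or in Years 2-5.

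Severity is low. The SAP reports one subject enrolled and enrollment terminated, so an enrollment hold no longer matters; what remains is prompt DMC review during any continuing follow-up of that subject. The documents give no frequency for AST-led or late-INR cases, so the number of affected cases cannot be estimated. The first point rests on the text alone. The size of the second rests on the assumed episode lengths and nominal visit timing.

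**What to change.** In Protocol 9.3.3.1:

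- Combined limb: *ALT or AST ≥ 3x ULN and (total bilirubin > 2x ULN or INR > 1.5)*.
- Symptom limb: *ALT or AST ≥ 3x ULN with signs and symptoms of liver dysfunction*.
- Extend the extra-hepatic exemption to ALT or AST elevations.
- Leave the limb at above 5x ULN on ALT.

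Every SAP 14.1.5 laboratory case would then meet the trigger unless exempt as extra-hepatic.

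Optionally, in the row of Table 9.7.8.3.2 for ALT at or above 3x ULN, repeat PT/INR with the liver tests while ALT stays at that level. An AST condition does not belong in that row, because an AST-led subject with ALT below 3x ULN never enters it. If one is wanted, it needs its own entry rule.

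Cost: three lines of wording, using an AST result already in every liver panel, and a few more DMC alerts, some from muscle-derived AST. The widened exemption limits these, and 9.4.8.2 already uses a concurrent CPK rise to recognise ALT elevations from exercise. The optional change adds one result, and possibly one tube, per draw. A separate AST rule would add twice-weekly draws in such cases if it mirrors the ALT row.
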